6.1.5. Per-Protocol (PP) Analysis Set

The per-protocol (PP) analysis set comprises all subjects in the FAS who have an OHSA#1 assessment at Week 4 obtained no earlier than study day 25 and no later than study day 42, did not use a prohibited medication during the treatment period, and did not meet any of the following criteria:

1. Poor study drug compliance, defined as compliance $< 80\%$ or $\geq 120\%$ over the interval from first to last dose during the treatment period

2. Did not meet efficacy-related inclusion criteria (criterion 5, OHSA#1 score \geq 4)
3. Took a prohibited medication prior to randomization (exclusion criterion 4, subject has used strong CYP1A2 inhibitors or inducers within 7 days or 5 half-lives before randomization or requires concomitant use until the follow-up visit; exclusion criterion 5, subject has changed dose, frequency, or type of prescribed medication for orthostatic hypotension within 7 days prior to randomization, or failed to taper off midodrine and droxidopa (if applicable) at least 7 days prior to randomization)
4. Received a treatment other than the randomized treatment

Subjects who used midodrine not per protocol will be excluded from the PP analysis set. Subjects who used midodrine as rescue therapy per the instructions in the protocol will be included in the PP analysis set, and OHSA#1 collected on the visits when rescue therapy was used (if any) will be censored.

A listing of FAS subjects excluded from the PP set will be provided, with reasons for exclusion.

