### 6.8.2. Subject Discontinuation

Any subject (or his or her legally authorized representative) may withdraw their consent to participate in the study at any time without prejudice. The Investigator must withdraw from the study any subject who requests to be withdrawn. A subject's participation in the study may be discontinued at any time at the discretion of the Investigator and in accordance with his or her clinical judgment. When possible, the tests and evaluations listed for the termination visit should be completed. If a subject withdraws before completing the study, the reason for withdrawal is to be documented on the CRF.

The sponsor will be notified of all subject withdrawals.

Reasons for which the Investigator may withdraw a subject from the study or a subject may choose to terminate participation before completion of the study include, but are not limited to, the following:

- Adverse Event
- Physician Decision
- Pregnancy
- Protocol Violation
- Withdrawal by Subject
- Other

The subject may also discontinue from the study if the study is discontinued by the Sponsor.

Subjects who discontinue study medication early because of an adverse reaction should be encouraged to continue their participation in the follow-up safety assessments. If a subject fails to return for scheduled visits, a documented effort must be made to determine the reason.

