**Orthostatic Hypotension Symptom Assessment (OHSA)**

Please circle the number on the scale that best rates how severe your symptoms from low blood pressure have been *on the average* over the past week. Please respond to every symptom. If you do not experience the symptom, circle zero (0). PLEASE RATE THE SYMPTOMS THAT ARE DUE ONLY TO YOUR LOW BLOOD PRESSURE PROBLEM

1. Dizziness, lightheadedness, feeling faint, or feeling like you might blackout  
 NONE 0 1 2 3 4 5 6 7 8 9 10 WORST POSSIBLE
2. Problems with vision (blurring, seeing spots, tunnel vision, etc.)  
 NONE 0 1 2 3 4 5 6 7 8 9 10 WORST POSSIBLE
3. Weakness  
 NONE 0 1 2 3 4 5 6 7 8 9 10 WORST POSSIBLE
4. Fatigue  
 NONE 0 1 2 3 4 5 6 7 8 9 10 WORST POSSIBLE
5. Trouble concentrating  
 NONE 0 1 2 3 4 5 6 7 8 9 10 WORST POSSIBLE
6. Head/neck discomfort  
 NONE 0 1 2 3 4 5 6 7 8 9 10 WORST POSSIBLE

THR173023\_0169\_OHQ\_English(US)\_v1.0\_2018\_Aug\_01.doc

Protocol: 0169													
Visit	Subject ID Number										Rater Initials		
	1	6	9	-							-		

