9.2. Extent of Exposure and Treatment Compliance

Duration of study drug exposure (days) will be summarized. Duration of exposure to study drug is calculated as (date of last dose – date of first dose + 1).

Subjects will receive their assigned dose (10-mg dose of amprelosetine (TD-9855) or matching placebo) once daily. Treatment compliance as a percentage of the expected total dose will be calculated as follows, using the information captured on the CRF page for “Study Drug Dispensing / Return”:

- $100 \times (\text{number of tablets dispensed} - \text{number of tablets returned}) / (\text{date of last dose} - \text{date of first dose} + 1)$

Treatment compliance as a percentage of expected total dose will be summarized by treatment group for the safety analysis set as a continuous variable and using the following categories, after rounding to the nearest 0.1%:

- $\geq 120\%$
- $\geq 80\% - < 120\%$
- $< 80\%$

Study drug administration (date/time and study day) and drug accountability data will be listed.

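### The per-protocol compliance filter stops at the last dose, so a subject who stops early and returns the unused tablets can enter the per-protocol analysis with an off-dosing Week 4 OHSA#1

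*SAP*

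**What the plan says.** SAP 6.1.5 builds the PP set from FAS subjects "who have an OHSA#1 assessment at Week 4 obtained no earlier than study day 25 and no later than study day 42". Criterion 1 then excludes "Poor study drug compliance, defined as compliance" below 80% or at or above 120%, evaluated "over the interval from first to last dose during the treatment period". SAP 9.2 gives the formula: tablets dispensed minus tablets returned, divided by the number of days from first to last dose inclusive, times 100.

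The other readable PP conditions concern prohibited medication, the entry OHSA#1 score, receipt of the randomized treatment, and midodrine. OHSA#1 is censored at visits where rescue midodrine was used. There is no matching rule for an OHSA#1 recorded after dosing has ended.

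Four other provisions matter:

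- SAP 6.3.4 assigns assessments to analysis visits by study day, whatever the visit was called in the database.
- The schedule of procedures collects the OHQ at Visit 6 or early termination (ET). For withdrawals, Protocol 6.8.2 adds: "When possible, the tests and evaluations listed for the termination visit should be completed". It sets no deadline relative to the last dose.
- The OHSA form (Protocol Appendix 2-1) asks for the number that "best rates how severe your symptoms from low blood pressure have been", on average, over the past week.
- SAP 8.3.2 describes the PP analysis as supplementary.

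**The concern.** A PP analysis is meant to show the effect in subjects who were treated as planned. A filter whose denominator ends at the last tablet taken can detect gaps before that tablet, but it cannot detect stopping. The days between the last dose and the Week 4 OHSA#1 are not counted as missed, and no other readable criterion requires completion of treatment or dosing near the assessment.

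Among the readable analyses of the primary endpoint, PP is the only one restricted by drug compliance. The tipping-point analysis deals with missing data; the others deal with visit modality and subgroups. If post-dosing scores enter the PP set, its estimate no longer describes subjects on treatment at the endpoint, and nothing in its definition would show this.

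**Working it through.** **Inputs.** Compliance interval and limits: SAP 6.1.5. Formula: SAP 9.2, whose denominator in days implies one tablet per day. Week 4 window, study days 25 to 42: SAP 6.1.5 and 6.3.4. Planned treatment, 4 weeks or 28 daily doses: SAP 4.2. Recall, one week: SAP 8.6.1. Planned difference 1.5, SD 3.0, power 90%, dropout 10%: Protocol 8.2.

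**Step 1: the formula for an early stopper.** Let the last dose fall on study day L, with no doses missed before then and all unused tablets returned. Written compliance = 100 × L / (L − 1 + 1) = 100% for every L.

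| Last dose (study day) | Written compliance | Share of 28 planned doses | Days since last dose at a day-28 OHSA#1 |
|---|---|---|---|
| 14 | 100% | 14/28 = 50.0% | 14 |
| 18 | 100% | 18/28 = 64.3% | 10 |
| 21 | 100% | 21/28 = 75.0% | 7 |
| 22 | 100% | 22/28 = 78.6% | 6 |
| 23 | 100% | 23/28 = 82.1% | 5 |

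**Step 2: the recall week.** Take the recall at study day 28 as study days 22 to 28. With a last dose on study day 21 or earlier, no tablet was taken on any of those days. The subject still passes criterion 1 and the timing condition.

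**Step 3: can such a score arise?** There are two routes:

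- An ET visit that falls on study day 25 or later. For example, last dose on day 18 and ET OHQ on day 26 gives a gap of 26 − 18 = 8 days and written compliance of 100%.
- A subject who stops tablets but keeps attending. Protocol 5.3 answers poor compliance with counseling and re-training; it does not require withdrawal.

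**Step 4: what the formula does catch.** The 100% result depends on tablets being returned. Assume 28 dispensed and none returned. A day-14 stop then scores 28/14 = 200% and a day-21 stop 28/21 = 133%. Both are excluded by the 120% limit.

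**Step 5: illustrative size.** First, the plan's design figures. By the normal approximation, n per arm = 2 × (1.960 + 1.282)² × (3.0/1.5)² = 84.1, rounded up to 85, or 170 in total; 170/0.9 = 189 randomized. The total is redacted, but SAP 4.4 equates 40% with at least 76 subjects, and 76/0.40 = 190, which agrees. With 190 × 0.9 = 171 evaluable subjects, power is 0.905.

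Now assume that a share p of active-arm PP subjects is off dosing with no residual effect. The difference becomes 1.5 × (1 − p). Power is shown for the same 171 subjects, for scale only, since the PP analysis carries no power claim.

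| p (assumed) | Difference | Power |
|---|---|---|
| 0 | 1.50 | 0.905 |
| 2% | 1.47 | 0.893 |
| 5% | 1.425 | 0.874 |
| 10% | 1.35 | 0.837 |

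The 10% row equals the whole planned dropout rate and is best read as an outer bound.

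**The case against.** The strongest reply is that the route is narrow and the analysis minor. Subjects who meet a stopping rule leave the study (Protocol 6.8.1). An ET questionnaire before study day 25 does not qualify for PP. The follow-up visit has no OHQ. The day-25 floor therefore removes early stoppers who are assessed promptly. Early stopping will also be visible in the exposure summary (SAP 9.2) and in disposition (SAP 7.2). All of this stands, and it is why the severity is low. It does not remove the gap, because none of it keeps a late post-dosing score out of the PP set.

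A reader might infer more than the documents support:

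- *That early stopping is the main form of non-exposure, or differs by arm.* Nothing in the documents says so.
- *That every early stopper enters the PP set.* This fails when tablets are not returned, or when no OHSA#1 falls in the window.
- *That off dosing means off drug.* The half-life is redacted, so residual effect cannot be judged.
- *That the report would certify the PP set as at least 80% compliant.* SAP 9.2 plans the compliance summary for the safety set.
- *That everyone with a last dose by study day 22 would fail an 80% limit run to the assessment.* This depends on the denominator: 22/28 = 78.6% fails, but 22/27 = 81.5% passes if no dose is due on the assessment day.

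**Conclusion.** The gap is real and follows directly from the text. Criterion 1 cannot register early stopping when unused tablets are returned, and no readable PP criterion ties the Week 4 OHSA#1 to the last dose. The protocol's major-deviation list (8.3.2) is redacted, but the readable SAP criteria do not refer to it.

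The consequence is limited to the PP analysis. It might be tempting to read this as a threat to the primary result. It is not: the FAS analysis follows randomized treatment and does not use the compliance filter, and PP lies outside the testing hierarchy in SAP 8.4.3. The number of subjects affected is probably small and cannot be derived from the documents. The dilution figures rest wholly on an assumed share and on no residual effect. This is a cheap improvement of low severity.

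**What to change.** Keep criterion 1 of SAP 6.1.5 and its 80% and 120% limits. Add one criterion based on dosing dates, not tablet counts. It should exclude a subject who stopped study drug before the end of the 4-week treatment period and whose last dose precedes the Week 4 OHSA#1 used in the analysis by more than a pre-specified number of days. That number should be shorter than the 7-day recall; the 3-day visit window is a natural choice. With 3 days, a last dose on study day 21 and OHSA#1 on day 28 (gap 7) is excluded. The SAP should state how the end of the treatment period is dated, so that a subject who stops quietly but keeps attending is judged by the last-dose date. Leave the SAP 9.2 summary as it is.

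Replacing the denominator of criterion 1 with the interval from first dose to OHSA#1 (date difference) would be worse, assuming 28 tablets dispensed:

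- A full completer, last dose on day 28 and assessed on day 37, would score 28/36 = 77.8% and be dropped with no dose missed.
- A day-14 stopper who returns nothing, assessed on day 28, would score 28/27 = 103.7% and be admitted; the present formula gives 200% and excludes.
- Stoppers on days 22 and 23 would still pass, at 22/27 = 81.5% and 23/27 = 85.2%.

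The cost is one sentence and one derived variable from dates already listed under SAP 7.2 and 9.2. The PP set becomes slightly smaller. Completers assessed late in the window stay in, as SAP 6.1.5 now intends.

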6.1.6. Examination of Subgroups

To assess consistency of treatment effect across subgroups, the primary analysis of OHSA#1 will be repeated for each of the following subgroups:

1. Disease Type: MSA, PD, and PAF
2. Gender: Male and Female
3. Timing of Primary Endpoint Visit Relative to COVID-19 Pandemic Onset:
Before 18MAR2020, On or After 18MAR2020

6.2. Baseline Definition

Unless stated otherwise, baseline is the last assessment (scheduled or unscheduled) obtained before the first dose of randomized study medication.

6.3. Derived and Transformed Data

6.3.1. Study Day

If the date of interest occurs on or after the date of the first dose, study day will be calculated as date of interest – date of first dose + 1.

If the date of interest occurs prior to the date of the first dose, study day will be calculated as date of interest – date of first dose. There is no study day 0.

In this study, subject will receive the first dose of study medication in the morning of the day following randomization and completion of baseline study assessments. Study day 1 for a subject in the analysis will be defined as the first day the subject receives study drug, which is different from the protocol definition of study day 1 as the day of randomization. To make it clear which definition is being used, in this document “Day x” (e.g., Day 1 [Visit 2]) refers to the protocol definition and “study day x” refers to study day relative to the date of the first dose.

6.3.2. Change from Baseline

Change from baseline is calculated as postbaseline result – baseline result.

If either the baseline or the postbaseline result is missing, the change from baseline is set to missing.

6.3.3. Body Mass Index (BMI)

BMI will be calculated as follows:

$$BMI(kg/m^2) = \frac{weight(kg)}{height(m)^2}$$

6.3.4. Analysis Visit Windows

Assessments that are summarized by visit will be assigned to analysis visits using the following analysis visit windows, without regard to the visit label associated with the assessment in the clinical database.

Table 3: Analysis Visit Windows

Analysis Visit	Analysis Visit Window	
	Start (study day)	Stop (study day)
For endpoints collected at Weeks 1, 2, 3, and 4, including C-SSRS, BSFC-s, OHSA, OHDAS, and vital signs		
Week 1 (study day 7)	2	10
Week 2 (study day 14)	11	17
Week 3 (study day 21)	18	24
Week 4 (study day 28)	25	42
For endpoints collected at Weeks 1 and 3, including ABPM position		
Week 1 (study day 7)	2	14
Week 3 (study day 21)	15	42
For endpoints collected at Weeks 2 and 4, including safety laboratory tests		
Week 2 (study day 14)	2	21
Week 4 (study day 28)	22	42
For endpoints other than PGI-C collected at Week 4, including EQ-5D, NMSS, HADS, UPDRS, PDQ-8, COMPASS-31, UMSARS, and ECG		
Week 4 (study day 28)	15	42
For PGI-C* (collected at Week 4)		
Week 4 (study day 28)	2	42

*All endpoints except PGI-C are also collected on or prior to study day -1. PGI-C, being a change assessment, is collected only at the Week 4 visit or early termination visit.

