### **6.3.6. Treatment Day 29 – Visit 6 / Early Termination**

The following procedures will be performed on the Day 29 visit (+/- 3 days) and the following procedures must be completed first, and in the order below:

1. Review concomitant medications and smoking usage
2. OHQ subject training
3. OHQ (OHSA and OHDAS)

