## 26. Collect and review study medication

### 6.3.7. Follow-up Day 43 – Visit 7

The follow-up visit is applicable only for those subjects that will not proceed to Study 0170 and will be completed two weeks from the date of the last dose.

The following procedures will be performed on the Day 43 visit (+/- 3 days):

The following procedures are listed in the recommended order, however flexibility for scheduling is permitted:

1. Review concomitant medications and smoking usage

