Following the screening period, the subject will proceed to Visit 2 to further confirm the additional eligibility criteria prior to randomization. This includes the completion of the Orthostatic Hypotension Questionnaire (OHQ) in which a minimum score of 4 points in OHS#1 is required. Subjects meeting all applicable inclusion criteria and none of the applicable exclusion criteria, including confirmation of relevant criteria by the independent Enrollment Steering Committee (ESC), will be randomized to receive either amprelosetine (TD-9855) or matching placebo for the next 4 weeks.

Following randomization and completion of study assessments, the subject will receive a [REDACTED] of amprelosetine (TD-9855) (or matching placebo) [REDACTED] for the remaining double-blind treatment period.

Subjects completing the 4-week double-blind treatment period will be eligible to enroll and continue receiving study medication in Study 0170. The final visit for those subjects who do not complete the 4-week double-blind treatment period or who choose not to continue into Study 0170 will be the follow-up visit (V7). This visit must be completed two weeks from the date of the last dose.

The subject will return for weekly assessments as outlined in the Schedule of Study Procedures (Table 2).

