- i. [REDACTED]
- k. Ambulatory blood pressure monitoring equipment will be provided to the subject during the screening visit. Beginning approximately 72 to 24-hours before a subject conducts the Day 1 (Visit 2), and before the Day 8 and Day 22 visits, subjects will put on the 24-hour blood pressure monitoring equipment and initiate the recording. Once the 24-hour session is complete, subjects will remove and return the equipment to the research center during the next visit. During each 24-hour session, the blood pressure monitoring device will be programmed to automatically measure blood pressure every 2 hours beginning at the top of the hour. During each 24-hour session, subjects should also maintain a log of their posture at the time of each blood pressure measurement. Details regarding the ambulatory monitoring will be provided in a separate manual.
- l. Study medication will be ingested in the morning at approximately the same time of day with 8 ounces of water. The exact time and day of dosing will be recorded on the mornings of study visits. Subjects should be reminded to maintain an adequate fluid intake during their scheduled visits.
- m. The assessments or procedures will be performed within 24-hours prior to subject taking the study medication (pre-dose). Following randomization and completion of study assessments, the subject will begin taking study medication on Day 2 in the morning.
- n. C-SSRS is to be completed following OHQ questionnaire from Visit 2 to Visit 6.
- o. Follow-up visit is only applicable for those subjects that do not proceed to Study 0170 and will be completed two weeks from the date of the last dose.
- p. The assessment should be performed at approximately (± 2 hour) the same time of day on Day 1 (except Screening). Subjects should abstain from eating for at least 90mins prior to this assessment.
- q. Valsalva maneuver is to be performed for PAF subjects only if no results are available within 24 months from the date of randomization.

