6.3.5. Multiple Assessments

In general, if multiple valid observations exist in the window of an analysis visit, the record to be included in the summary and analyses will be chosen on the following basis, unless otherwise specified:

- The record closest to the nominal visit

If records are equidistant or distance cannot be determined:

- The latest record

If records have the same date/time:

- The average

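### SAP Table 3 has no Follow-up analysis visit, so Visit 7 safety values are tabulated as treatment weeks or not at all, and early-termination ECGs before study day 15 enter no by-visit table

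*SAP*

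**What the plan says.** SAP 6.3.4 states that assessments summarised by visit are "assigned to analysis visits using the following analysis visit windows, without regard to the visit label associated with the assessment in the clinical database". In Table 3 the group that names C-SSRS and vital signs has four windows: Week 1 (study days 2-10), Week 2 (11-17), Week 3 (18-24) and Week 4 (25-42), with nominal study days 7, 14, 21 and 28. Weight is not named, but the list is open-ended and SAP 9.5 summarises weight at each visit.

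ECG belongs to another group, "For endpoints other than PGI-C collected at Week 4, including EQ-5D, NMSS, HADS, UPDRS, PDQ-8, COMPASS-31, UMSARS, and ECG", whose single window is study days 15-42. PGI-C, likewise collected only at Week 4 or ET, has a window from study day 2.

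If several records fall in one window, SAP 6.3.5 takes "The record closest to the nominal visit", and the latest if they are equidistant.

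Under SAP 6.3.1 the "subject will receive the first dose of study medication in the morning of the day following randomization", so study day equals protocol Day minus 1.

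Visit 7 applies to early terminators and to completers who do not enter Study 0170 (SAP 4.1). It "will be completed two weeks from the date of the last dose" (SAP Table 2, footnote o), with a tolerance of 3 days either way. Protocol 6.3.7 lists C-SSRS, vital signs and weight at this visit, and no OHQ, PGI-C or ECG.

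SAP 9.7 plans C-SSRS summaries for every visit at which the items are collected. SAP 9.6 presents the ECG outlier table by visit. Protocol 8.6 plans safety summaries by nominal visit or over the whole treatment period.

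**The concern.** Visit 7 is an off-drug visit, but Table 3 gives it nowhere to go except a treatment-week row. Where it lands depends only on when the subject stopped. An early stopper's Visit 7 tends to fall in a later week in which nothing else was recorded, so it is tabulated as that week. A completer's Visit 7 shares the Week 4 window with Visit 6 and loses to it, or falls after study day 42.

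The Week 2-4 rows for vital signs, weight and C-SSRS can therefore mix treatment-period values with values taken about 14 days after last dose, and the reader cannot tell them apart. Completers' follow-up values do not appear in any by-visit table, contrary to what SAP 9.7 promises for C-SSRS.

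The ECG gap concerns subjects who leave early. ECG is scheduled after baseline only at Visit 6/ET, so an ET ECG in the first two weeks is that subject's only scheduled post-baseline tracing, and the by-visit summary and outlier table leave it out.

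**Working it through.** **Check on the day arithmetic.** Protocol Day 29 is study day 29 - 1 = 28, which matches the Week 4 nominal day in Table 3. Day 29 + 14 = Day 43, which is the protocol's Visit 7 day and equals study day 42. The Visit 6 window of Day 29 ± 3 is study days 25-31.

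**Early terminators, last dose on study days 1-24.** Let L be the study day of last dose. Visit 7 is on day L + 11 to L + 17, giving 24 × 7 = 168 day combinations, all between study days 12 and 41 and so always inside a Week 2, 3 or 4 window. The ET visit is on day L + d. Each combination is passed through Table 3 and the SAP 6.3.5 selection rule. Visit 7 is the record used as follows:

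| ET delay d (days) | Week 2 | Week 3 | Week 4 | Total of 168 |
|---|---|---|---|---|
| 0 | 21 | 49 | 98 | 168 (100%) |
| 1 | 21 | 49 | 91 | 161 (96%) |
| 3 | 21 | 49 | 77 | 147 (88%) |
| 7 | 19 | 47 | 53 | 119 (71%) |
| 10 | 12 | 40 | 40 | 92 (55%) |

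In the remaining combinations the ET record shares the window and is nearer the nominal day. No on-treatment record competes: with L at most 24 the Week 4 window has not yet opened, and the Week 2 and 3 windows are 7 days wide against a lag of at least 11 days.

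**Early terminators, last dose on study days 25-27.** There are 3 × 7 = 21 combinations, and Visit 7 is used in none at any of these delays: 18 lose to ET and 3 fall after day 42.

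**Completers not entering Study 0170, Visit 6 value present.** Visit 6 is on study days 25-31 (7 values), last dose is 0, 1, 2 or 3 days before it, and Visit 7 is 11-17 days after last dose (7 values): 4 × 49 = 196 combinations.

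| Last dose before Visit 6 (days) | Loses to Visit 6 | After study day 42 | Used |
|---|---|---|---|
| 0 | 28 | 21 | 0 |
| 1 | 34 | 15 | 0 |
| 2 | 39 | 10 | 0 |
| 3 | 43 | 6 | 0 |
| Total | 144 | 52 | 0 of 196 |

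An on-schedule Visit 7 on day 42 is inside the Week 4 window but 14 days from the nominal day, while Visit 6 is at most 3 days from it. If the Visit 6 value is missing, Visit 7 becomes the Week 4 value in those 144 combinations.

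**ECG.** The window opens on study day 15, so an ET ECG on days 2-14 matches no row.

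**Illustrative subject numbers.** The sample size, stopping days and Visit 7 attendance are not visible. SAP 4.4 gives at least 76 subjects as 40%, so 76 / 0.40 = 190 randomized. This agrees with protocol 8.2: a difference of 1.5, SD 3.0, 90% power and two-sided 0.05 give 85 per arm, and 170 / 0.9 = 189. At 10% dropout, about 19 subjects stop early. Assume last dose uniform over days 1-27 (27 × 7 = 189 combinations), ET delay 0 to 7 days and 50-70% attendance:

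- Any Week 2-4 row: 19 × 168/189 = 16.9 down to 19 × 119/189 = 12.0. Multiplied by 0.5-0.7, about 6-12 subjects.
- Week 4 row alone: 19 × 98/189 = 9.9 down to 19 × 53/189 = 5.3, giving about 3-7 subjects.
- ET ECG on days 2-14: 19 × 13/27 = 9.1 down to 19 × 7/27 = 4.9, giving about 2-6 subjects.

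**The case against.** The strongest objection is that little depends on these tables. Safety analyses are descriptive, all values are listed, SAP 9.6 has a separate QTcF listing not tied to a window, and protocol 7.2 requires clinically significant abnormalities to be recorded as adverse events. SAP 9.5 flags vital-sign outliers in the listing and does not say that its outlier summary is by visit, so Visit 7 outliers may still be counted there. All of this stands and is why the point is minor.

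The counts are also conditional. The documents set no limit on the ET delay, and protocol 6.8.2 asks for termination tests only when possible; at 10 days the share falls to 55%. The completer result needs a Visit 6 value. Blood pressure and heart rate are summarised by body position, so selection could differ between supine and seated rows. Day combinations are not probabilities, and the subject numbers are assumptions. These are fair limits on size, but they do not change where the windows send a given record.

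It can be said that SAP 9.7, being specific, overrides Table 3 for C-SSRS. But it defines no Follow-up analysis visit, so at best the two sections conflict. Windowing by time since first dose is a legitimate choice, and protocol 8.1 lets the SAP change planned summaries. Even so, a row labelled as a treatment week should not silently include off-drug values. Appendix 1 of the SAP, on changes from the protocol, is redacted, so nothing is inferred from it. An explanation there would not add the missing row to Table 3.

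**Conclusion.** The concern holds, at minor severity. Applied as written, Table 3 labels Visit 7 vital signs, weight and C-SSRS as Week 2, 3 or 4 for most early terminators: 71-100% of day combinations when last dose is on study days 1-24 and ET follows within 7 days. It leaves them out of every by-visit table for completers who decline Study 0170 and have a Visit 6 value. ET ECGs on study days 2-14 are left out of the by-visit ECG summary and outlier table. The inclusion of weight rests on reading the Table 3 list as open-ended.

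On the illustrative assumptions above, about 6-12 subjects would have a follow-up value in a treatment-week row, with 17 as the bound at full attendance, and about 2-6 ECGs would be left out. The direction of any distortion is unknown. Adverse-event, laboratory and efficacy analyses are unaffected.

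**What to change.** - **SAP 6.3.4:** add a Follow-up analysis visit for vital signs, weight and C-SSRS. It takes records collected at Visit 7, as a stated exception to the rule that ignores labels, and those records are excluded from the Week 1-4 windows. Visit 6/ET records stay in the weekly windows.
- **SAP 9.6:** add an any-post-baseline row to the ECG outlier table that includes every Visit 6/ET ECG whatever its study day. This avoids labelling an early tracing as Week 4.
- **SAP 9.7:** summarise C-SSRS separately for the treatment period and for Follow-up.
- **Consistency:** reconcile 6.3.4 with the nominal-visit wording of protocol 8.6.

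The cost is one row and one sentence in 6.3.4, one row in the ECG outlier table and two C-SSRS summary blocks. No new data are needed.
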